APPENDIX C

The following adverse events are expected as disease-related events (i.e. related to acute myocardial infarction):

Arrhythmias

All arrhythmias occurring later than 3 hours after fibrinolysis
All arrhythmias in patients who did not receive fibrinolysis

Ischaemia and symptoms of coronary artery disease

Angina pectoris (stable)
Angina pectoris (unstable)
Back pain (of cardiac origin)
Cardiac enzymes (abnormal)
Cardiac markers (abnormal)
Chest pain
Electrocardiogram abnormalities
Myocardial ischaemia
Myocardial reinfarction
Recurrent myocardial ischaemia
ST-elevation
Substernal chest pain
Substernal pain

Artery disorders

Aortic dissection
Coronary artery dissection
Coronary artery disorder
Coronary artery thrombosis
Coronary occlusion
Vascular anomaly

Cardiac failure

Acute pulmonary oedema
Cardiogenic shock
Congestive heart failure
Cor pulmonale
Heart failure
Left heart failure

Pulmonary oedema
Haemodynamic and circulatory shock

Pericardium disorders

Pericardial effusion
Pericarditis

Other cardiac disorders

Acute mitral regurgitation
Acute ventricular septum defect
Cardiac rupture
Cardiomyopathy
Electro-mechanical dissociation

Other events

Deep thrombophlebitis
Hypertension
Livedo reticularis
Peripheral oedema
Peripheral vascular disorder
Syncope
Thrombocytosis
Vascular disorder
Venous thrombosis

## **HISTORY**

Version	Date	Change
1.0	06/09/2022	- Original version
1.1	21/09/2022	

- Limits “additional in-hospital events” to serious in-hospital events (Section 6.6, Table 15.1) to match output of STREAM 1.

- Clarifies in Section 6.6 that PCI (after study PCI) is a planned intervention. It is not recorded if the PCI actually took place.

- Deletes subgroup analyses for safety endpoints

- Deleted multiple imputation sentence and adapted test in Section 9.1.4.1.

1.2	17/11/2022	- Adapted ECG endpoints

## **LIST OF ABBREVIATIONS**

Abbreviation	Description
AE	Adverse event
CABG	Coronary Artery Bypass Grafting
CHF	Congestive Heart Failure
ECG	Electrocardiogram
EMD	Electro-Mechanical Dissociation
eGFR	estimated Glomerular Filtration Rate
FAS	Full analysis set
ICH	Intracranial hemorrhage
ICU	Intensive Care Unit
ITT	Intention-To-Treat
mmHg	millimeter of mercury
PhI	Pharmaco-invasive
PCI	Percutaneous Coronary Intervention
PPCI	Primary Percutaneous Coronary Intervention
PES-I	Pooled elderly set – Intention-to-treat
PES-P	Pooled elderly set – Per Protocol
PPS	Per protocol set
Q1	Lower quartile
Q3	Upper quartile
SD	Standard deviation
TSAP	Trial statistical analysis plan
TIMI	Thrombolysis In Myocardial Infarction

## 1 Introduction

This statistical analysis plan for STREAM 2 contains the following:

1. Definition of the analysis populations
2. Handling of missing data
3. Statistical methods
4. Tables and Figures

## 2 Trial design

STREAM 2 is an open-label, prospective, randomized (2:1), parallel, comparative international multi-centre trial which randomises patients  $\geq 60$  yrs with acute ST-elevation myocardial infarction within 3 hours of onset of symptoms to:

- A. a pharmaco invasive (PhI) strategy of early fibrinolytic treatment with half-dose tenecteplase and additional antiplatelet therapy with a loading dose of 300 mg clopidogrel, aspirin and coupled with antithrombin therapy followed by catheterisation within 6-24 hours or rescue coronary intervention as required (PI therapy);
- B. a strategy of primary PCI (PPCI) with a P2Y12 antagonist and antithrombin treatment according to local standards.

The principal aim of the trial is to evaluate the efficacy and safety in the 2 treatment groups measured by ST-segment resolution, TIMI flow grades, and clinical events.

The trial is a hypothesis-generating study. No confirmatory statistical hypothesis is pre-specified. All statistical tests are of exploratory nature based on descriptive statistics for formal statistical hypotheses generation.

## 3 Sample size justification

Approximately 600 elderly patients were planned to be randomized with 400 receiving PI therapy and 200 PPCI. A minimum of approximately 100 patients  $\geq 70$  years of age will be randomized to the PhI arm. The aim was to combine ECG and angiographic data from the latter group with similar data from STREAM-1, in order to have a more reliable estimate of the efficacy of the PhI strategy in elderly patients.

Although the study of 600 patients is not powered to show a difference in clinical events, given the elderly nature of the population there will be ample efficacy and safety events to observe. They will be reported along with their 95% confidence limits.

If the study would turn into a confirmatory trial after the interim analysis (see Section 7), a primary hypothesis on a combined clinical endpoint will be pre-specified.

## **4 Definition of the Analysis Populations**

The analysis population is defined as follows:

### **Full analysis set (FAS)**

based on randomized treatment:

Subjects will be analysed according to the treatment group to which they were randomized, irrespective of which study treatment was given or if any study treatment was received.

### **Per Protocol Set (PPS)** based on randomized treatment:

Analysis of the FAS excluding patients who had major protocol violations. These include among others: not receiving the allocated treatment, violation of important inclusion/exclusion criteria, receiving an inappropriate dose of study medication, not receiving tenecteplase or primary PCI in a timely manner and receiving concomitant treatments not allowed per protocol.

The Per Protocol Set will be reviewed and finalized prior to database lock during a blinded to outcome data review meeting. The decision which patients will be excluded will be taken on a case by case basis blinded to outcome data by relevant members of the study team, including at least (but not limited to) the Executive Committee Chairmen and the Study Statistician.

All major protocol deviations that lead to exclusion from the PPS will be fully documented in the Analysis Sets Specification Document that will be dated and signed prior to database lock.

## **Pooled Elderly Set – Intention to treat (PES-I)**

The combined sets of the following subjects:

- Patients  $\geq 75$  years from STREAM 2
- Patients  $\geq 75$  years from STREAM 1 who are randomized after protocol amendment 2.

Subjects will be analysed according to the treatment group to which they were randomized.

## **Pooled Elderly Set – Per protocol (PES-P)**

The combined sets of the following subjects:

- Patients  $\geq 75$  years from STREAM 2 who belong to the PPS
- Patients  $\geq 75$  years from STREAM 1 who belong to the PPS and are randomized after protocol amendment 2.

Subjects will be analysed according to the treatment group to which they were randomized

Given that no per protocol set was defined in STREAM I, during the blinded review meeting also the relevant patients of STREAM I will be reviewed blinded to outcome in order to include them in the PES-P set. All major protocol deviations that lead to exclusion from the PES-P will be fully documented in Analysis Sets Specification Document that will be dated and signed prior to database lock.

The primary efficacy and safety analyses will be based on FAS. The PPS will serve for sensitivity analyses. The PES-I and PES-P will be used to have a more reliable estimate of the efficacy and safety of the PhI strategy in elderly patients for a selection of endpoints (see Section 9).

## **5 Handling of Missing Data**

Best efforts will be made to collect complete data for the clinical endpoints of interest, regardless of whether or not the subject received study drug/treatment. In order to minimize bias and take all randomised patients into the analysis when the proportion of missing data for a specific endpoint is larger than 1%, a multiple imputation analysis will be performed. Only endpoints listed in Sections 6.1 to 6.4, with the exception of the ECG endpoint Sum ST-segment deviation

resolution 30-min post-angiogram/PCI, will be imputed, if necessary. No imputation for the endpoints listed in Section 6.5 will be performed.

The baseline covariates age, sex, assigned treatment, body weight, infarct location (anterior or other), previous infarction, Killip class, heart rate, systolic blood pressure and time from symptom onset to randomisation, hypertension, diabetes, place of randomization, Q-wave, time of randomization (before or after protocol amendment 5), time of randomization to administration of tenecteplase or sheath insertion and type of access together with all single efficacy and safety endpoints, ECG (with the exception of the endpoint Sum ST-segment deviation resolution 30-min post-angiogram/PCI) and angiographic endpoints will be multiply imputed using the fully conditional specification (FCS) method using a regression or logistic regression model, whichever is applicable. Note that for the ECG endpoint successful reperfusion, the imputation will be done on the ST-segment resolution from which successful reperfusion will be determined. For mortality, the variables cardiac and non-cardiac mortality instead of overall mortality will be used. For non-intracranial bleeds, only the variables major and minor non-intracranial bleeds will be put in the model. Total non-intracranial bleeds will be determined later on. For stroke, the variables total stroke, will be put in the model. The subclassifications of ischaemic, intracranial haemorrhage, fatal, non-fatal, disabling, non-disabling will be done in a second phase in which the type will be imputed by a random draw from a binary distribution with a probability of success equal to the maximum of the observed event rate or 0.01 stratified by assigned treatment

Before the large imputation will take place, the following procedure will be applied. In case it is known that a patient died, but the cause is unknown, cardiac or non-cardiac mortality will be first determined by imputing the cause by a random draw from a binary distribution with a probability of success equal to the maximum of the observed event rate or 0.01 stratified by assigned treatment.

The value 12345 will be used as seed for all the imputations. In case of computational problems for the large imputation model, primarily 5 times different seed values will be used augmenting the seed number by 1 (12345 to 12349). If computational problems persist, the endpoint with the fewest number of overall events is deleted from the imputation scheme and handled separately later on. In case there are several variables with the same small number of

events, the variable which comes first in the alphabetical order will be omitted first. The same procedure with at most 5 random seeds is tried again with one variable less in the imputation scheme. This process is iterated until a successful multiple imputation has been obtained. The endpoint(s) that has (have) been omitted from the imputation scheme will be imputed by a random draw from a binary distribution with a probability of success equal to the maximum of the observed event rate or 0.0001 stratified by assigned treatment. Combined endpoints will be constructed based on the imputed single endpoints. A total of 100 imputations will be performed. The default number of burn-in iterations will be applied.

For all other endpoints, best efforts will be made to collect complete data for the events of interest. All percentages will be calculated on the number of subjects with non-missing information.

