Aborted myocardial infarction⁵⁴ will be assessed by means of ECG as ST-segment resolution relative to baseline value and cardiac marker enzymes as done previously in STREAM-1⁵⁵. Peak levels of troponin I/T (CK/CK-MB) will be collected at baseline, and 8-12 hrs and 24 hrs after randomisation. Quantification of aborted myocardial infarction will be defined as troponin values \leq 5 times the upper limit of normal (ULN) within 24 hours of randomisation (or CK/CK-MB levels \leq 2 times ULN). Only peak values of markers of necrosis (expressed as times exceeding the upper limit of normal) will be recorded in the eCRF; the complete set of measured values will however be kept in the source documents.

Rescue PCI post PPI therapy

If ST-segment resolution is $<50\%$ relative to the ST-segment elevation in the qualifying lead at baseline, irrespective of the presence or absence or clinical symptoms

Refractory ischaemia

Symptoms of ischaemia with ST-deviation or definite T-wave inversion persisting for at least 10 min despite medical management while in-hospital and not fulfilling the diagnosis of infarction.

Major arrhythmias

Sustained ventricular tachycardia (ventricular tachycardia lasting ≥ 30 seconds or requiring cardioversion or causing symptoms/hypotension), ventricular fibrillation, asystole, atrial fibrillation, 2nd and 3rd degree atrio-ventricular block.

Invasive procedures

Include CABG, PTCA, stent placement, intra-aortic balloon.

Other major cardiac events

Other major cardiac events include sustained hypotension, acute mitral regurgitation, acute ventricular septum defect, pericarditis, pulmonary embolism and tamponade.

Sustained hypotension

SBP < 90 mmHg for > 30 minutes

Rehospitalisation for cardiac reasons

If, after discharge, a patient is readmitted to the hospital until day 30 due to cardiac reasons, this information must be recorded in the eCRF. Any event requiring unscheduled readmission will be considered a serious adverse event (SAE) and recorded as described in section 5.2.1. Only if readmission was scheduled, e.g. because of a routine or planned procedure, will the event leading to rehospitalisation not be considered as a serious adverse event.

Rehospitalisation for non-cardiac reasons

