#### **6.1.3 Combined ECG and clinical endpoints**

- Incidence of aborted myocardial infarction (in both groups)
- Need for rescue PCI/revascularization as determined by investigator in Group A.

- Need for rescue PCI/revascularization as determined by central adjudication in Group A

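### The imputation model for aborted MI leaves out the cardiac markers that help define it, and SAP 5 has no rule for deriving the endpoint from its parts

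*SAP*

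**What the plan says.** SAP 6.1.3 lists aborted MI, in both groups, among the efficacy endpoints of primary interest. SAP 8.5.3.1 analyses it by relative risk as in 8.5.1, with results combined over imputations where applicable. It also feeds the subgroup tables (Table 16.1.3) and the pooled elderly analyses (9.1.3.1).

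SAP 5 sets the trigger: "when the proportion of missing data for a specific endpoint is larger than 1%, a multiple imputation analysis will be performed". It sets the scope: "Only endpoints listed in Sections 6.1 to 6.4, with the exception of the ECG endpoint Sum ST-segment deviation" resolution. Aborted MI is therefore in scope. The fully conditional specification (FCS) model contains a list of baseline and procedural covariates ending with "time of randomization to administration of tenecteplase or sheath insertion and type of access together with all single efficacy and safety endpoints, ECG" and angiographic endpoints. No cardiac marker is named.

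For several other endpoints SAP 5 works through the parts. For reperfusion, "the imputation will be done on the ST-segment resolution from which successful reperfusion will be determined". Death enters as cardiac and non-cardiac, and non-intracranial bleeds as major and minor with the total derived later. The general rule is "Combined endpoints will be constructed based on the imputed single endpoints". Nothing specific is said about aborted MI.

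Protocol Appendix B2 states that aborted MI "will be assessed by means of ECG as ST-segment resolution relative to baseline value and cardiac marker enzymes". It then adds: "Quantification of aborted myocardial infarction will be defined as troponin values" at or below 5 times the upper limit of normal (ULN) within 24 hours, or CK/CK-MB at or below 2 times ULN. It gives no ST-resolution cut-off and no ECG time. Peak markers, as multiples of ULN, are recorded in the eCRF, and SAP Table 8.1 tabulates them with class boundaries at exactly 2 and 5.

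**The concern.** An endpoint that is a function of two recorded quantities should be imputed with both in view. Here one of the two is left out of the model, although it is collected. A patient may lack the ECG but have a recorded peak above the limit, in which case the status is already known. Another may lack the ECG but have a low marker, in which case aborted MI is far more likely than in the average patient. A model without the marker cannot tell these two apart. At stake is the relative risk for one of the endpoints of primary interest, in a section of the SAP whose stated purpose is to reduce bias.

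**Working it through.** The plan has no figure to reproduce: it gives no aborted-MI rate, missing rate, power or effect size. From the documents come the planned arms of 400 and 200 (Protocol 7.5) and the trigger, 0.01 × 600 = 6, so imputation starts above 6 missing. Everything else below is assumed. Markers are taken as always observed and only ECGs as missing. The other covariates are taken as uninformative.

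Notation: q = share with a low marker; s = share of low-marker patients meeting the ST criterion; m = share of ECGs missing. True rate = q × s.

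**Coding A: one yes/no, missing whenever the ECG is missing.** Imputed rate = events observed / patients observed.
- Assume q = 0.16 (PhI) and 0.14 (PPCI), s = 0.90. True rates are 0.144 and 0.126; RR = 1.14; expected events 57.6 + 25.2 = 82.8.
- Loss unrelated to the marker, m = 0.15. Ruled-out patients drawn as events: 400 × 0.15 × 0.84 × 0.144 + 200 × 0.15 × 0.86 × 0.126 = 7.3 + 3.3 = about 10.5 per imputed dataset. The arm rates are not biased.
- Precision. Complete-data variance of log RR = 0.856/57.6 + 0.874/25.2 = 0.0495. Coding A does no better than complete cases: 0.0495/0.85 = 0.0583, SE 0.241. With the marker used, the variance per arm is (1−q)/(nq) + (1−s)/(nqs(1−m)): 0.0152 + 0.0354 = 0.0506, SE 0.225. Ratio 1.07. The same formula gives about 1.02 at 5% missing and 1.13 at 25%.
- Loss related to the marker, PPCI only: 5% missing if low, 20% if high (PhI 10% in both). PPCI rate = (0.14 × 0.95 × 0.90)/(0.14 × 0.95 + 0.86 × 0.80) = 0.1197/0.821 = 0.146, so RR = 0.144/0.146 = 0.99. With the arms reversed, PhI = (0.16 × 0.95 × 0.90)/(0.16 × 0.95 + 0.84 × 0.80) = 0.1368/0.824 = 0.166, so RR = 0.166/0.126 = 1.32. Truth in both: 1.14.

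**Coding B: a high marker is set to not aborted; low-marker patients without an ECG are imputed as yes/no without the marker.** Imputed rate = qs(1−m)/(1−qm).
- q = 0.10, s = 0.90, true 9.0%. At m = 0.10: 0.081/0.99 = 8.2%. At m = 0.20: 0.072/0.98 = 7.3%.
- Arms with q = 0.15 and 0.10, m = 0.05 and 0.20: 0.12825/0.9925 = 12.9% and 7.3%, RR 1.76 against a true 0.135/0.090 = 1.50.

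**Coding C: built from parts, with ST resolution imputed without the marker.** Low-marker patients without an ECG receive the overall ST rate instead of s.
- PhI, ST criterion met in 90% of low-marker and 78% of high-marker patients: overall 0.16 × 0.90 + 0.84 × 0.78 = 0.799. At m = 0.15: 0.16 × (0.85 × 0.90 + 0.15 × 0.799) = 0.1416 against 0.144, an undercount of 1.7%.
- A patient whose marker is missing has no imputed marker limb to build from.

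**With the marker in the model and the endpoint derived**, the true rate is recovered in every scenario, because low-marker patients are imputed at s and high-marker patients are fixed as not aborted.

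**The case against.** A reader might infer that the plan will create impossible aborted MIs and so bias the endpoint. The documents do not support that. It requires aborted MI to be imputed as one yes/no and to be coded missing despite an observed high marker, and neither is stated. SAP 6.1.3 sits under a heading for combined endpoints, and the rule in SAP 5 that such endpoints are built from imputed single endpoints points rather to coding C, where a high marker gives not aborted. Protocol 5.5 sends the clinical and ECG data for aborted infarction to central adjudication, and an adjudicator holding a high marker could settle the status without the ECG. Appendix B2 can also be read as a marker-only definition, under which a missing ECG does not matter.

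It is fair, too, that the model is not blind. It contains ST resolution, TIMI flow, infarct location, Q-wave, Killip class and the clinical events, several of which plausibly track infarct size. The relative-risk shifts above use none of these and assume fourfold marker-dependent loss in one arm only. Even then the shift is about 0.15 on the log scale, or 0.6 of the standard error of 0.241.

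These points limit the harm, but they do not close the gap. The SAP does not say which coding applies, and under every reading that uses both limbs the listed model ignores one of them. Codings B and C avoid impossible events and can still put the rate too low.

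**Conclusion.** The point holds as an avoidable weakness in SAP 5: aborted MI can be imputed, the model has none of the markers that help define it, and no derivation rule is given. What follows depends on the coding.
- One yes/no: lost precision, plus bias in either direction if ECG loss depends on the marker.
- High marker set to not aborted, or built from parts: no impossible events, but the rate can be too low. On the assumed inputs the relative undercount is about 2% (coding C, 15% missing) to 18% (coding B, 20% missing: 7.3% against 9.0%).

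The actual size cannot be stated, because missing rates, marker distribution and aborted-MI rates are not in the documents. If no more than 1% is missing, nothing is imputed. If loss is unrelated to the marker, the yes/no coding costs only precision. The trial is hypothesis-generating, so what is affected is an estimate of primary interest, not a confirmatory test. The change is worth making because it is nearly free and follows what SAP 5 already does for reperfusion, death and bleeds.

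**What to change.** In SAP 5:
1. Add the recorded peak-marker class (troponin above 5 times the upper limit, or CK/CK-MB above 2 times where that is the marker used) to the FCS model.
2. State which ECG and which ST-resolution cut-off define the ST limb of aborted MI, or state that the definition is marker-only.
3. Derive aborted MI in each imputed dataset from ST resolution and marker class, not as a separately imputed yes/no.
4. Set it to not aborted, without imputation, whenever an observed limb already fails.
5. Say how a centrally adjudicated status is used when one limb is missing.

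The cost is one existing variable, a derivation step in the program and a few sentences in the SAP; no new data are needed. The drawback is one more variable in an already large model, which slightly raises the chance of the computational problems for which SAP 5 has a fallback. If the marker class replaces a directly imputed yes/no, the number of variables does not grow.

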7.3 HANDLING OF MISSING DATA

No imputation of missing data is foreseen. Best efforts will be made to collect complete data for the clinical events of interest. Distribution of the missing data will be checked across groups.

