7.5 DETERMINATION OF SAMPLE SIZE

As mentioned before this is a hypothesis generating trial. No primary hypothesis or primary endpoint have been formulated. Approximately 600 patients are planned to be randomized with 400 receiving PhI therapy and 200 PPCI. A minimum of approximately 100 patients \geq 70 years of age will be randomized to the PhI arm. The aim is to combine ECG and angiographic data from the latter group with similar data from STREAM-1^{16, 18} in order to have a more reliable estimate of the efficacy of the PhI strategy in elderly patients. The analysis of ECG data, angiographic data and clinical events will be described in detail in the statistical analysis plan. Although the study of 600 patients is not powered to show a difference in clinical events, given the elderly nature of the population there will be ample efficacy and safety events to observe. They will be reported along with their 95% confidence limits. For reference, in patients \geq 60 years from STREAM-1 the 30 day composite of death, shock, heart failure and re-MI ranged between 18 and 20 % for PhI and PPCI groups. Bleeding data in this age group were 1.7 % and 0 % ICH and 8.8 % and 7 % non-intracranial major bleeding respectively. If the study would turn into a confirmatory trial after the interim analysis a primary hypothesis on a combined clinical endpoint will be pre-specified.

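### The SAP's joint logistic imputation is open to separation for rare and mutually exclusive endpoints, and the trigger for its fallback is undefined, so imputed event rates can be far too high

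*SAP*

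**What the plan says.** Protocol section 7.3 states: "No imputation of missing data is foreseen". SAP section 5 plans multiple imputation for any endpoint in sections 6.1 to 6.4 with more than 1% missing, except the sum ST-deviation endpoint. The list of covariates ends "and type of access together with all single efficacy and safety endpoints, ECG" and angiographic endpoints. All of these "will be multiply imputed using the fully conditional specification (FCS) method using a regression or logistic regression model, whichever is applicable".

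Three further rules in SAP section 5 matter here:

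- Death is split: "For mortality, the variables cardiac and non-cardiac mortality instead of overall mortality will be used".
- Up to five seeds are tried if the joint model fails. After that: "If computational problems persist, the endpoint with the fewest number of overall events is deleted from the imputation scheme and handled separately later on". A dropped endpoint is drawn at its observed rate by arm, and the process repeats until an imputation succeeds.
- Composite endpoints are assembled from the imputed single endpoints.

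The SAP mentions no augmentation, penalisation or predictor selection, and no restriction on which variable may predict which. It does not say whether a run that finishes despite separation counts as a computational problem. The per-protocol set is the only sensitivity analysis that SAP section 4 names.

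**The concern.** A logistic model is separated when some combination of predictors divides events from non-events perfectly. The maximum-likelihood estimate then does not exist, and the reported coefficients are large with very large variances. Imputation draws coefficients around that fit. Such draws give patients with missing outcomes probabilities near 0 or 1 almost at random, so a rare event is imputed far too often.

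The two death variables make this certain. Nobody who died of a cardiac cause also died of a non-cardiac cause, so each variable has an empty cell in the other's model. That cell is in the observed data, and a new seed cannot fill it. Nothing in the scheme stops one patient from being imputed both deaths.

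The composite of primary interest is the union of death, shock, CHF and reinfarction, so excess events in each component accumulate. Rescue PCI (SAP 6.1.3) and 60–90 minute reperfusion (SAP 6.2) exist only in Group A, yet section 5 does not exempt them. Read literally, they are missing for every PPCI patient.

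At stake are the endpoint of primary interest and the rare safety endpoints whenever the 1% threshold is passed, above all if missingness differs between the arms of this open-label trial.

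**Working it through.** The documents give no imputed rate, expected missing share or component event counts, so there is no figure of theirs to reproduce.

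**Model size (SAP 5 and 6.1–6.4).** There are 17 items listed as baseline. There are 13 single clinical endpoints: two deaths, shock, CHF, reinfarction, two rehospitalisations, total stroke, major bleed, minor bleed, transfusion and two ventricular fibrillation items. There are about 6 ECG, rescue and angiographic variables. 17 + 13 + 6 = 36, so about 35 predictors per model before dummy coding.

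**Documented sparsity (Protocol 7.5).** "Approximately 600 patients are planned to be randomized with 400 receiving PhI therapy and 200 PPCI". The STREAM-1 reference for patients of 60 years or older is a 30-day "composite of death, shock, heart failure and re-MI ranged between 18 and 20 % for PhI and PPCI groups", and bleeding of "1.7 % and 0 % ICH and 8.8 % and 7 % non-intracranial major bleeding respectively".

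- Composite: 0.18 to 0.20 × 600 = 108 to 120 events, shared among its components.
- Major non-intracranial bleeding: 0.088 × 400 + 0.07 × 200 = 35.2 + 14 ≈ 49.
- ICH: 0.017 × 400 + 0 × 200 ≈ 7. ICH is imputed in a second step and is not itself in the joint model; the count only shows how sparse stroke events are.

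**Simulation (assumed inputs).** n = 600 at 2:1. Events were about 37 cardiac deaths, 7 non-cardiac deaths, 32 shock, 51 CHF and 10 reinfarction; other endpoints had about 5 to 75. All 30-day endpoints were missing at random in 1.5% or 3% of patients. Coefficients were drawn from a normal distribution centred on the logistic fit, with the inverse information as variance. There were 10–20 burn-in cycles. The true composite rate among missing patients was about 0.13–0.18.

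| Behaviour | Imputed composite among missing |
|---|---|
| Full model, plain ML | 0.95 (0.79–1.00 across data sets) |
| Same, 1.5% missing / 20 burn-in cycles | 0.96 / 0.97 |
| Same, fits stopped at 8 iterations / vital status known | 0.84 / 0.85 |
| Plain ML, repeat runs | 0.74–0.95 |
| 17 baseline items plus five components only | 0.59 |
| Fallback with 3 endpoints dropped | 0.58 |
| Full model, augmented likelihood | 0.50–0.53 |
| 11 predictors, the two deaths still predicting each other | 0.42 |
| Fallback on every separation (6–11 dropped) | about 0.24 (0.19–0.28) |

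The last row treats components as independent, so it may be slightly high. Under the full model, 3–15% of missing patients received both deaths.

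**Is it the number of predictors?** With 35 dense predictors and one endpoint:

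| Events | True rate | Imputed |
|---|---|---|
| 5 | 0.008 | 0.49 |
| 10 | 0.017 | 0.11 |
| 15 | 0.025 | 0.06 |
| 30 | 0.050 | 0.08 |
| 50 | 0.083 | 0.11 |

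Except at the lowest counts, inflation is modest. The severe inflation comes from separation: very few events, sparse binary endpoints used as predictors, and the two death variables.

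**Effect on the reported rate.** Shift = missing share × (imputed rate − observed rate).

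- Per 1% missing, at 0.50 versus 0.20: 0.01 × 0.30 = 0.3 points.
- 3% missing, plain ML: 0.177 + 0.03 × (0.95 − 0.177) = 0.200.
- 3% missing, augmented: 0.177 + 0.03 × (0.53 − 0.177) = 0.188.
- 3% missing, fallback on separation: 0.177 + 0.03 × (0.24 − 0.177) = 0.179.
- 4% versus 1% missing by arm, augmented: 0.03 × (0.53 − 0.18) ≈ 1.05 points of spurious risk difference.

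**The case against.** A reader might infer that the plan gives the composite to roughly half of the missing patients. The documents do not fix that figure. One half is a single point between about 0.24 and 0.97, and the position depends on software behaviour that the SAP leaves open and on assumed event counts. The simulation only approximates the SAS procedure. A reader might also blame the 35 predictors as such, and the dense-predictor check does not bear that out.

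The fallback deserves credit. If separation triggers it repeatedly, it brings the imputed composite close to the observed rate. Missing deaths should be few, because Protocol 6.3 collects 30-day vital status after withdrawal and SAP section 5 resolves unknown causes of known deaths first. Even so, knowing vital status left 0.85 under plain ML.

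SAP 8.12 plans Kaplan–Meier and cumulative incidence curves from observed events, so not everything is imputed. These are curves, though, not the planned relative risk and risk difference without imputation. Treating the Group A-only endpoints as missing in PPCI is one reading; not applicable is the more natural one, but the SAP does not say so. The protocol defers analysis detail to the SAP, so departing from section 7.3 is not in itself an error.

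On size, with 20% events and 400:200 the 95% half-width of the risk difference is 1.96 × √(0.16/400 + 0.16/200) ≈ 6.8 points, well above a 1-point shift.

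**Conclusion.** The concern stands as a should-fix. Followed as written, the scheme has separation built in for the two death variables and likely separation for other rare endpoints. It can produce impossible double deaths, and its remedy depends on an undefined trigger. Under the assumed rates, the imputed composite among missing patients runs from about 0.24 (six or more endpoints dropped), through about 0.5 (augmented likelihood), to 0.74–0.97 (plain ML accepted), against 16–18% observed.

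The effect on the whole-trial rate is bounded by the missing share: about 1 to 2.5 points at 3% missing unless the fallback fires on separation, when it is about 0.2 points. Differential missingness of 1% versus 4% adds about 1 point to the risk difference under augmented likelihood. Missing shares and component counts are assumptions, and at or below 1% missing the issue does not arise.

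A stronger reading, that the main comparison is invalid or that the fallback cannot work, is not supported. The trial is exploratory with no confirmatory hypothesis, and the plan's own fallback largely works if separation is made to trigger it.

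**What to change.** Amend SAP section 5:

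1. Impute all-cause death first, then the cause only among the dead.
2. Limit each clinical-endpoint model to a few predictors with an augmented or penalised likelihood. Augmentation alone left about 0.5, and fewer predictors with both deaths retained left 0.42, so this is needed together with item 1. Alternatively, impute the composite, or its components jointly, by arm-specific draws with parameter uncertainty. Independent component draws are not a safe substitute: they ignore correlation within patients and gave 0.21 against 0.16 in one set of runs.
3. Define computational problems to include separation and non-existent maximum-likelihood estimates.
4. State that rescue PCI and 60–90 minute reperfusion are not imputed in PPCI and stay out of the joint model.
5. Report the complete-case analysis, in line with Protocol 7.3, beside the imputed one for the section 6.1 endpoints, and compare imputed with observed rates by arm.

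The cost is SAP wording and code, which becomes simpler. The downside is a slightly less rich missing-at-random model. The richer predictor set can be kept for ST resolution, which is imputed as a continuous measure.
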